5.3.5.2 Adverse Events Occurring Secondary to Other Events

In general, adverse events occurring secondary to other events (e.g., cascade events or clinical sequelae) should be identified by their primary cause, with the exception of severe or serious secondary events. However, medically significant adverse events occurring secondary to an initiating event that are separated in time should be recorded as independent events on the Adverse Event eCRF. For example:

- If vomiting results in mild dehydration with no additional treatment in a healthy adult, only vomiting should be reported on the eCRF.
- If vomiting results in severe dehydration, both events should be reported separately on the eCRF.
- If a severe gastrointestinal hemorrhage leads to renal failure, both events should be reported separately on the eCRF.
- If dizziness leads to a fall and subsequent fracture, all three events should be reported separately on the eCRF.
- If neutropenia is accompanied by a mild, non-serious infection, only neutropenia should be reported on the eCRF.
- If neutropenia is accompanied by a severe or serious infection, both events should be reported separately on the eCRF.

All adverse events should be recorded separately on the Adverse Event eCRF if it is unclear as to whether the events are associated.

5.3.5.3 Persistent or Recurrent Adverse Events

A persistent adverse event is one that extends continuously, without resolution, between patient evaluation timepoints. Such events should only be recorded once on the Adverse Event eCRF. The initial severity of the event should be recorded, and the severity should be updated to reflect the most extreme severity any time the event worsens. If the event becomes serious, the Adverse Event eCRF should be updated to reflect this.

A recurrent adverse event is one that resolves between patient evaluation timepoints and subsequently recurs. Each recurrence of an adverse event should be recorded separately on the Adverse Event eCRF.

5.3.5.4 Abnormal Laboratory Values

Not every laboratory abnormality qualifies as an adverse event. A laboratory test result should be reported as an adverse event if it meets any of the following criteria:

- Is accompanied by clinical symptoms
- Results in a change in study treatment (e.g., dosage modification, treatment interruption, or treatment discontinuation)
- Results in a medical intervention (e.g., potassium supplementation for hypokalemia) or a change in concomitant therapy

- Is clinically significant in the investigator's judgment

It is the investigator's responsibility to review all laboratory findings. Medical and scientific judgment should be exercised in deciding whether an isolated laboratory abnormality should be classified as an adverse event.

If a clinically significant laboratory abnormality is a manifestation of a disease or syndrome (e.g., alkaline phosphatase and bilirubin 5 × ULN associated with cholecystitis), only the diagnosis (i.e., cholecystitis) should be recorded on the Adverse Event eCRF.

If a clinically significant laboratory abnormality is not a manifestation of a clearly discernible disease or syndrome, the abnormality itself should be recorded on the Adverse Event eCRF, along with a descriptor indicating if the test result is above or below the normal range (e.g., "elevated potassium," as opposed to "abnormal potassium"). If the laboratory abnormality can be characterized by a precise clinical term per standard definitions, the clinical term should be recorded as the adverse event. For example, an elevated serum potassium level of 7.0 mEq/L should be recorded as "hyperkalemia."

Observations of the same clinically significant laboratory abnormality from visit to visit should not be repeatedly recorded on the Adverse Event eCRF, unless the etiology changes. The initial severity of the event should be recorded, and the severity or seriousness should be updated any time the event worsens.

5.3.5.5 Abnormal Vital Sign Values

Not every vital sign abnormality qualifies as an adverse event. A vital sign result should be reported as an adverse event if it meets any of the following criteria:

- Accompanied by clinical symptoms
- Results in a change in study treatment (e.g., dosage modification, treatment interruption, or treatment discontinuation)
- Results in a medical intervention or a change in concomitant therapy
- Clinically significant in the investigator's judgment

It is the investigator's responsibility to review all vital sign findings. Medical and scientific judgment should be exercised in deciding whether an isolated vital sign abnormality should be classified as an adverse event.

If a clinically significant vital sign abnormality is a sign of a disease or syndrome (e.g., high blood pressure), only the diagnosis (i.e., hypertension) should be recorded on the Adverse Event eCRF.

Observations of the same clinically significant vital sign abnormality from visit to visit should not be repeatedly recorded on the Adverse Event eCRF, unless the etiology

changes. The initial severity of the event should be recorded, and the severity or seriousness should be updated any time the event worsens.

5.3.5.6 Abnormal Liver Function Tests

The finding of an elevated ALT or AST ($>3 \times$ the baseline value) in combination with either an elevated total bilirubin ($>2 \times$ ULN) or clinical jaundice in the absence of cholestasis or other causes of hyperbilirubinemia is considered to be an indicator of severe liver injury. Therefore, investigators must report as an adverse event the occurrence of either of the following:

- Treatment-emergent ALT or AST $>3 \times$ the baseline value in combination with total bilirubin $>2 \times$ ULN (of which $\geq 35\%$ is direct bilirubin)
- Treatment-emergent ALT or AST $>3 \times$ the baseline value in combination with clinical jaundice

The most appropriate diagnosis or (if a diagnosis cannot be established) the abnormal laboratory values should be recorded on the Adverse Event eCRF (see Section 5.3.5.1) and reported to the Sponsor within 24 hours after learning of the event, either as a serious adverse event or a non-serious adverse event of special interest (see Section 5.4.2).

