In a Phase I trial (Study CA 184161, sponsored by Bristol-Myers Squibb), asymptomatic Grade 3 increases in transaminases and bilirubin occurred with concurrent administration of ipilimumab (3 mg/kg) and vemurafenib (960 mg BID or 720 mg BID) ([Ribas et al. 2012](#)). All liver laboratory abnormalities were asymptomatic and reversible with permanent discontinuation of the study drugs or, in some cases, administration of corticosteroids. On the basis of these data, concurrent administration of ipilimumab and vemurafenib is not recommended outside of a clinical trial. Full details are provided in the Vemurafenib IB.

An assessment of liver-related adverse events reported with vemurafenib use showed that 63 cases of medically confirmed serious adverse events were drug-induced liver injury (DILI) on the basis of clinical chemistry criteria from the DILI Expert Working Group ([Aithal et al. 2011](#)). Of the 63 cases, two were assessed as severe; both were reported as hepatic failure. The outcome of both cases of hepatic failure have been reported to be completely resolved following vemurafenib discontinuation. There were no reported deaths among the 63 cases of liver injury. The median time to onset of the adverse events was 44 days after initial dose. The median ALT to alkaline phosphatase ratio was 1.5, suggesting a trend toward cholestatic pattern of liver injury. There were no risk factors or populations at risk identified.

A review of the Roche safety database found neutropenia to be an uncommon (6 cases per 1000 person-years, 0.6%) adverse drug reaction associated with the use of vemurafenib, often occurring during the first 6–12 weeks of treatment. It appears to be reversible—usually within 2 weeks—with temporary interruption, dose reduction, or discontinuation and, in some cases, was managed with GM-CSF.

A safety review completed in 2014 identified pancreatitis as an adverse drug reaction in patients treated with vemurafenib. Seventeen cases of pancreatitis with no strong risk factors or alternative explanations were reported. Eight of the seventeen cases were assessed as likely associated with vemurafenib use on the basis of event onset latency and rechallenge/dechallenge information. The clinical presentation in terms of severity, mild to moderate, was consistent with the clinical picture of drug-induced pancreatitis ([Lankisch et al. 1995](#)).

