4.5.1.8 Laboratory Assessments

Blood samples for hematology, coagulation screening studies, liver function tests, serum chemistry, pregnancy test, and hepatitis B and C serology will be analyzed at the study site's local laboratory. Stool for occult blood will be analyzed at the local site. Blood and tumor tissue samples for biomarker and PK studies will be sent to one or several Roche-designated central laboratories or to the Sponsor for analysis. Instruction manuals and supply kits will be provided for all central laboratory assessments. All screening laboratory assessments should be obtained prior to initiation of study drug at Cycle 1, Day 1.

Laboratory assessments will include the following:

- Hematology: Hemoglobin, hematocrit, platelet count, WBC, WBC differential (absolute neutrophil count, lymphocyte, monocyte, eosinophil, and basophil counts and other cells)
- Coagulation: PT, INR, and aPTT
- Serum chemistry: urea (BUN), creatinine, sodium, potassium, chloride, bicarbonate, glucose, phosphorus, magnesium, total calcium, serum albumin, LDH, and uric acid

- Liver function tests: ALT, AST, total bilirubin, and alkaline phosphatase
- Pregnancy test: All women of childbearing potential (including those who have had a tubal ligation) will have a serum pregnancy test at screening and every 3 cycles (i.e., Cycles 3, 6, 9, and 12 or every 12 ± 2 weeks), starting from Cycle 1, Day 1, and at 12 ± 2 weeks and 26 ± 2 weeks after the last dose of study drug. Urine pregnancy tests will be performed as needed. If a urine pregnancy test is positive, it must be confirmed by a serum pregnancy test.
- Viral serology/detection: Hepatitis B (hepatitis B surface antigen [HBsAg] and total hepatitis B core antibody [anti-HBc]) and HCV antibody
- Stool for occult blood

4.5.1.9 ***BRAF*^{V600} Mutation Testing**

Assessment of *BRAF*^{V600} mutation status of primary tumor tissue will be investigated using the **cobas**[®] BRAF V600 Mutation Test. A formalin-fixed paraffin-embedded (FFPE) tumor block or at least five serially cut, unstained tumor tissue slides (5 μm -thick sections) from one block will be collected at screening from consented patients. Patients whose tumors test positively for the *BRAF*^{V600} mutation will be eligible for enrollment in the clinical study if they meet other eligibility criteria.

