5.1.2.3.6 Hepatic Toxicity

Liver injury (ALT $\geq 5 \times$ ULN, ALT $\geq 3 \times$ ULN with bilirubin $\geq 2 \times$ ULN, or alkaline phosphatase $\geq 2 \times$ ULN with GGT elevation), including severe cases of liver injury (described as hepatic failure), has been reported in patients treated with vemurafenib. All patients will undergo liver function testing (i.e., AST, ALT, total bilirubin, and alkaline phosphatase) at periodic intervals while receiving study treatment (see Appendix 1). In addition, Grade 4 elevations of AST, ALT, serum bilirubin OR cases of elevated ALT or AST in combination with either an elevated bilirubin or clinical jaundice, (as defined in Section 5.3.5.6) qualifies as a non-serious adverse event of special interest and must be reported to the Sponsor within 24 hours after learning of the event.

Guidelines for interruption/dose reduction of study drug in the setting of liver function abnormality are provided in Table 2. Please note that all Grade 2 liver function test abnormalities will be defined as “intolerable” for the purposes of interruption/dose reduction of study drug.

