5.2.3 Non-Serious Adverse Events of Special Interest (Immediately Reportable to Roche)

Non-serious adverse event of special interest are required to be reported by the investigator to the Sponsor within 24 hours after learning of the event (see Section 5.4.2 for reporting instructions). Adverse events of special interest for this study include the following:

- Grade ≥ 3 photosensitivity
- Grade 4 elevations of AST, ALT, serum bilirubin OR cases of elevated ALT or AST in combination with either an elevated bilirubin or clinical jaundice, as defined in Section 5.3.5.6
- cuSCC (including KA)
- Grade ≥ 3 QT interval prolongation
- Gastrointestinal polyps
- Suspected transmission of an infectious agent by study drug

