Appendix 1 Schedule of Assessments (cont.)

prior to the start of the 90-day screening period and found to be normal, need not be repeated at screening.

- ^p For patients with personal history of adenomatous colon polyps or colorectal cancer, family history of colon cancer in which a first- and/or second-degree relative has been diagnosed with colorectal cancer at or after the age of 60 years, or signs or symptoms that could be related to colon cancer as determined by the site investigator or designee, colonoscopy to the cecum, with adequate bowel preparation, will be performed by a gastroenterologist or his or her designee who is experienced in the colonoscopic diagnosis of colorectal polyps and colorectal cancer (within the 90-day screening period). For select patients (described above), the screening colonoscopy is not required if colonoscopy to the cecum with adequate bowel preparation and adequate resection of all visualized polyps was performed within 1 year of the start of the 90-day screening period, unless the site investigator deems it necessary. All patients must have colonoscopy within 3 months of discontinuation of study drug. All polyps found at the screening or subsequent colonoscopies will need to be adequately resected. Please note that a patient with a personal history of more than three (> 3) adenomatous colorectal polyps or a personal history of adenomatous colorectal polyp(s) > 2 cm in size will be excluded from this study; this also applies to the screening colonoscopy for the select patients described above (see Section 4.1.2).
- ^q Stool sample will be collected at screening, Cycle 6, Day 1 (± 2 weeks), and at the end-of-treatment visit (± 2 weeks). If the stool occult sample is positive at screening, the patient must be cleared for study inclusion by a gastroenterologist or appropriately trained designee.
- ^r Includes hemoglobin, hematocrit, platelet count, WBC count, WBC differential (ANC), lymphocyte, monocyte, eosinophil, and basophil counts, and other cell counts.
- ^s Includes sodium, potassium, chloride, bicarbonate, glucose, BUN or urea, creatinine, calcium, total bilirubin, albumin, ALT, AST, alkaline phosphatase, phosphorus, magnesium, LDH, and uric acid.
- ^t If a patient discontinues study drug early, a serum pregnancy test will be performed at 12 ± 2 weeks and 26 ± 2 weeks after the last dose of study drug (except in the case of withdrawal of consent or loss to follow-up).

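### One limb of the 24-hour liver AESI needs a direct-bilirubin result that the schedule never collects, and no planned by-arm table of collected data shows concurrent transaminase and bilirubin elevation

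*Protocol*

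**What the plan says.** Protocol 5.2.3 lists the liver AESI, reportable within 24 hours. It begins "Grade 4 elevations of AST, ALT, serum bilirubin OR cases of elevated ALT or AST" and continues with an elevated bilirubin or clinical jaundice, as defined in 5.3.5.6. That gives three limbs:

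- **Grade 4:** AST, ALT or bilirubin at Grade 4, alone.
- **Laboratory combination (5.3.5.6, first bullet):** treatment-emergent ALT or AST above 3 x baseline "in combination with total bilirubin $>2 \times$ ULN (of which $\geq 35\%$ is direct bilirubin").
- **Jaundice combination (5.3.5.6, second bullet):** "Treatment-emergent ALT or AST $>3 \times$ the baseline value in combination with clinical jaundice".

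The opening sentence of 5.3.5.6 gives the combination with total bilirubin above 2 x ULN but no direct fraction, and says that it "in the absence of cholestasis or other causes of hyperbilirubinemia is considered to be an indicator of severe liver injury".

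The scheduled panel in 4.5.1.8 is "Liver function tests: ALT, AST, total bilirubin, and alkaline phosphatase". Section 5.1.2.3.6 names the same four tests. Appendix 1, footnote s, agrees: "total bilirubin, albumin, ALT, AST, alkaline phosphatase, phosphorus, magnesium, LDH, and uric acid". None lists direct bilirubin or GGT.

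Section 5.1.2.3.6 describes liver injury reported with vemurafenib in three forms: ALT at least 5 x ULN; ALT at least 3 x ULN with bilirubin at least 2 x ULN; or "alkaline phosphatase $\geq 2 \times$ ULN with GGT elevation". Section 1.2.5, on 63 serious cases of drug-induced liver injury, says: "The median ALT to alkaline phosphatase ratio was 1.5, suggesting a trend toward cholestatic pattern of liver injury".

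**The concern.** A reporting trigger should be decidable from the data the protocol collects, and here one limb is not. Two further features narrow what the AESI captures: transaminases are scaled to the patient's own baseline, and the alkaline phosphatase/GGT pattern that the protocol reports is in no limb.

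What is at stake is a comparable liver count by arm. The quarterly DSMB tables listed in Protocol 5.1.2.2 cover disposition, adverse events, serious events, deaths, discontinuations, AESIs and exposure, but no laboratory data. SAP 4.7.4 summarises baseline and worst grade for each laboratory parameter separately. A patient with ALT and bilirubin raised together therefore appears as a combined signal only if the AESI captures it.

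**Working it through.** There is no sample-size or power figure to reproduce, because the point concerns a definition. The check has three steps.

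**1. Analytes needed against analytes scheduled.** The laboratory combination needs ALT or AST, total bilirubin and direct bilirubin. Sections 4.5.1.8 and 5.1.2.3.6 and Appendix 1 supply all but the last. The alkaline phosphatase form in 5.1.2.3.6 needs GGT, which is also on no list.

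**2. The baseline multiple in ULN units.** Trigger = 3 x baseline. Entry allows ALT and AST up to 2.5 x ULN (Protocol 4.1.1). The comparison is with the ALT part of the 5.1.2.3.6 combination, at least 3 x ULN.

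| Baseline (x ULN) | Trigger (x ULN) | Against 3 x ULN |
|---|---|---|
| 0.5 | above 1.5 | more sensitive |
| 1.0 | above 3.0 | essentially equal |
| 1.5 | above 4.5 | stricter |
| 2.0 | above 6.0 | stricter |
| 2.5 | above 7.5 | stricter |

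The trigger also passes the stand-alone 5 x ULN level once baseline exceeds 5 / 3 = 1.67 x ULN.

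**3. Illustrative patients.** The documents do not print the Grade 4 cut-offs. I assumed 10 and 20 x ULN for ALT, with the same results at both, and assumed that bilirubin of 3 x ULN is below Grade 4. AST is taken as not meeting a limb by itself. Values are multiples of ULN.

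Liver injury as described in 5.1.2.3.6, but not an AESI:

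- ALT 8, bilirubin 1, baseline ALT 0.6: no bilirubin rise or jaundice, and below Grade 4.
- ALT 6, bilirubin 3, baseline ALT 2.5: 6 is below 3 x 2.5 = 7.5, so it fails even with jaundice.
- Alkaline phosphatase 4 with raised GGT, ALT 1.5, bilirubin 1, baseline ALT 0.6: 1.5 is below 3 x 0.6 = 1.8.
- ALT 6, bilirubin 3, baseline ALT 0.6, direct bilirubin not measured, no jaundice: ALT passes (6 against 1.8), but the limb cannot be established.

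Still caught:

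- The last patient, if jaundiced or if a 60% direct fraction is measured.
- ALT 25 alone.
- Alkaline phosphatase 4 with raised GGT, when ALT is 2.5 on a baseline of 0.6 and bilirubin is 3 with a 60% direct fraction.

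**The case against.** The strongest reply is that 5.3.5.6 is meant to be narrow. It targets severe injury without cholestasis, while the list in 5.1.2.3.6 describes what has been reported with the drug and is not this trial's AESI standard. This stands: being narrower than 5.1.2.3.6 is not in itself an error. It does not explain a condition on an unscheduled analyte, or why the opening sentence and the first bullet of one section differ.

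Second, other routes remain. The jaundice and Grade 4 limbs need no direct bilirubin. Local laboratories could measure it when an event is worked up. All Grade 2 liver test abnormalities count as intolerable for the interruption and dose-reduction rules in Table 2, and a laboratory result that changes treatment must be reported as an adverse event (5.3.5.4). Serious events go to the sponsor within 24 hours regardless. This also stands, so a reader who infers that the trial misses liver injury outright goes too far. The gap is in non-serious AESI reporting and in the combined count.

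Third, a reader might infer from the median ratio of 1.5 that half of the 63 historical cases would have escaped. The documents do not support that. Those cases were serious events, already expedited by another route, and a ratio at or below 1.5 does not show that a case fails the AESI limbs.

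Fourth, a reader might infer that the baseline multiple generally lowers sensitivity. It does so only for baselines above ULN.

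Finally, it is tempting to substitute the 5.1.2.3.6 list for the rule. That would lose cases, because the list contains neither AST nor jaundice. AST 4 x ULN from a baseline of 0.8 x ULN (3 x 0.8 = 2.4), with ALT 2 x ULN, alkaline phosphatase below 2 x ULN and jaundice, is an AESI now and would not be under the list. For a baseline of 0.5 x ULN, the combination's ALT threshold would rise from 1.5 to 3 x ULN.

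**Conclusion.** The point holds in limited form. One of three limbs cannot be evaluated from scheduled data. For patients entering above ULN, the ALT/AST threshold rises to as much as 7.5 x ULN. No limb covers the alkaline phosphatase/GGT pattern, and GGT is not scheduled. Some liver injury as described in 5.1.2.3.6 can therefore be absent from non-serious AESI reporting and from the AESI count by arm.

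The number of patients affected cannot be computed: the documents give no baseline ALT distribution and no rate of unscheduled direct-bilirubin testing. Net under-reporting is not shown, since the baseline rule gains cases below ULN and loses them above it. The illustrative results rest on the Grade 4 assumptions stated above. The clearest findings are the unscheduled analyte and the lack of any planned concurrent-elevation table.

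**What to change.** 1. **SAP 4.7.4.** Add a by-arm table, derived from the collected ALT, AST, total bilirubin and alkaline phosphatase, of (a) patients with concurrent ALT or AST and total bilirubin elevation, shown both against ULN and against baseline and without the direct-bilirubin condition; and (b) patients with alkaline phosphatase at least 2 x ULN. State what counts as concurrent, for example the same sample. In (b), separate patients already at that level at baseline, since entry allows 2.5 x ULN. The SAP already handles local normal ranges, so ULN multiples can be derived without new samples.
2. **Protocol 4.5.1.8, 5.1.2.3.6, 5.2.3, 5.3.5.6 and Appendix 1.** Reconcile these so that the AESI combination can be evaluated from the analytes collected. Keep AST and the clinical-jaundice limb, and do not substitute the 5.1.2.3.6 list.

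The cost is one extra descriptive safety table, with no effect on any efficacy test. It should be labelled as added after the primary analysis (cutoff 17 April 2017). Protocol wording now has little effect: the last dose was on 14 September 2016 and routine adverse event reporting ends 28 days later, on 12 October 2016. The SAP table is the change that can still alter an output.
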